## 11 ADVERSE EVENT REPORTING REQUIREMENTS

### 11.1 Definitions

#### 11.1.1 Adverse Event (AE)

An adverse event (AE) is any undesirable sign, symptom or medical condition or experience that develops or worsens in severity after starting the first dose of study treatment or any procedure specified in the protocol, even if the event is not considered to be related to the study.

Abnormal laboratory values or diagnostic test results constitute adverse events only if they induce clinical signs or symptoms or require treatment or further diagnostic tests.

#### 11.1.2 Serious adverse event (SAE)

A serious adverse event (SAE) is any adverse event, occurring at any dose and regardless of causality that:

- Results in death
- Is life-threatening. Life-threatening means that the person was at immediate risk of death from the reaction as it occurred, i.e., it does not include a reaction which hypothetically might have caused death had it occurred in a more severe form.
- Requires or prolongs inpatient hospitalization (i.e., the event required at least a 24-hour hospitalization or prolonged a hospitalization beyond the expected length of stay). Hospitalization admissions and/or surgical operations scheduled to occur during the study period, but planned prior to study entry are not considered SAEs if the illness or disease existed before the person was enrolled in the trial, provided that it did not deteriorate in an unexpected manner during the trial (e.g., surgery performed earlier than planned).
- Results in persistent or significant disability/incapacity. Disability is defined as a substantial disruption of a person's ability to conduct normal life functions.
- Is a congenital anomaly or birth defect; or
- Is an important medical event when, based upon appropriate medical judgment, it may jeopardize the participant and require medical or surgical intervention to prevent one of the outcomes listed above. Examples of such medical events include allergic bronchospasm requiring intensive

CONFIDENTIAL

This document is confidential. Do not disclose or use except as authorized.

treatment in an emergency room or at home; blood dyscrasias or convulsions that do not result in inpatient hospitalization, or the development of drug dependency or drug abuse.

Events **not** considered to be serious adverse events are hospitalizations for:

- routine treatment or monitoring of the studied indication, not associated with any deterioration in condition, or for elective procedures
- elective or pre-planned treatment for a pre-existing condition that did not worsen
- emergency outpatient treatment for an event not fulfilling the serious criteria outlined above and not resulting in inpatient admission
- respite care

### 11.1.3 Expectedness

Adverse events can be 'Expected' or 'Unexpected.'

#### 11.1.3.1 Expected adverse event

Expected adverse events are those that have been previously identified as resulting from administration of the agent. For the purposes of this study, an adverse event is considered expected when it appears in the current adverse event list, the Investigator's Brochure, the package insert or is included in the informed consent document as a potential risk.

Refer to Section 6 for a listing of expected adverse events associated with the study agent(s).

#### 11.1.3.2 Unexpected adverse event

For the purposes of this study, an adverse event is considered unexpected when it varies in nature, intensity or frequency from information provided in the current adverse event list, the Investigator's Brochure, the package insert or when it is not included in the informed consent document as a potential risk.

### 11.1.4 Attribution

Attribution is the relationship between an adverse event or serious adverse event and the study treatment. Attribution will be assigned as follows:

- Related – There is reasonable evidence that the AE is related to the study treatment.
- Unrelated - The AE is clearly NOT related to the study treatment.

CONFIDENTIAL

This document is confidential. Do not disclose or use except as authorized.

## 11.2 Procedures for AE and SAE Recording and Reporting

Participating investigators will assess the occurrence of AEs and SAEs at all participant evaluation time points during the study.

All AEs and SAEs whether reported by the participant, discovered during questioning, directly observed, or detected by physical examination, laboratory test or other means, will be recorded in the participant's medical record and on the appropriate study-specific case report forms.

The descriptions and grading scales found in the revised NCI Common Terminology Criteria for Adverse Events (CTCAE) version 4.0 will be utilized for AE reporting. All appropriate treatment areas should have access to a copy of the CTCAE version 4.0. A copy of the CTCAE version 4.0 can be downloaded from the CTEP website at:

[http://ctep.cancer.gov/protocolDevelopment/electronic\\_applications/ctc.htm](http://ctep.cancer.gov/protocolDevelopment/electronic_applications/ctc.htm).

## 11.3 Reporting Requirements

Each participating investigator is required to abide by the reporting requirements. The study must be conducted in compliance with FDA regulations, local safety reporting requirements, and reporting requirements of the principal investigator.

Each investigative site will be responsible to report SAEs that occur at that institution to their respective IRB. It is the responsibility of each participating investigator to report serious adverse events to the PI of this study, [name], and/or others as described below.

## 11.4 Reporting to the Study Sponsor

### 11.4.1 Serious Adverse Event Reporting

All serious adverse events that occur after the initial dose of study treatment, during treatment, or within 30 days of the last dose of treatment must be reported to the Principal Investigator, [name], on the local institutional SAE form. This includes events meeting the criteria outlined in Section 11.1.2, as well as the following:

- Grade 2 (moderate) and Grade 3 (severe) Events – Only events that are unexpected and related with the intervention.
- All Grade 4 (life-threatening or disabling) Events – Unless expected AND specifically listed in the protocol as not requiring reporting.

CONFIDENTIAL

This document is confidential. Do not disclose or use except as authorized.

- All Grade 5 (fatal) Events – When the participant is enrolled and actively participating in the trial OR when the event occurs within 30 days of the last study intervention.

Note: If the participant is in long term follow up, report the death at the time of continuing review.

Participating investigators must report each serious adverse event to the Principal Investigator [name] within 24 hours of learning of the occurrence. In the event that the participating investigator does not become aware of the serious adverse event immediately (e.g., participant sought treatment elsewhere), the participating investigator is to report the event within 24 hours after learning of it and document the time of his or her first awareness of the adverse event. Report serious adverse events by, email to:

Email: [[contact]](mailto:[contact])

Within the following 24-48 hours, the participating investigator must provide follow-up information on the serious adverse event. Follow-up information should describe whether the event has resolved or continues, if and how the event was treated, and whether the participant will continue or discontinue study participation.

Coordinating center will fax or email serious adverse events (initial and follow-up reports) to Astex Drug Safety within 24 hours of receiving SAE report to:

Astex Drug Safety

North America Local [contact]

North America Toll-Free [contact]

Email: [[contact]](mailto:[contact])

Astex Pharmaceuticals will provide a quarterly listing of all SAEs received to Sidney Kimmel Comprehensive Cancer Center at Johns Hopkins for comparison with the Sponsor's listing. Any missing SAEs or any discrepancies will be reported at that time.

#### **11.4.2 Non-Serious Adverse Event Reporting**

Non-serious adverse events will be reported to the Principal Investigator [name] on the toxicity Case Report Forms.

### **11.5 Reporting to the Institutional Review Board (IRB)**

CONFIDENTIAL

This document is confidential. Do not disclose or use except as authorized.

Other investigative sites should report serious adverse events to their respective IRB according to the local IRB's policies and procedures in reporting adverse events. A copy of the submitted institutional SAE form should be forwarded to:

[name]

Email: [contact]

The Principal Investigator [name] will submit SAE reports from outside institutions to the SKCCC IRB per their policies and procedures in reporting adverse events.

### **11.6 Reporting to the Food and Drug Administration (FDA)**

The Principal Investigator [name], as holder of the IND, will be responsible for all communication with the FDA. [name] will report to the FDA, regardless of the site of occurrence, any adverse event that is serious, unexpected and related to the study treatment (Suspected Unexpected Serious Adverse Reactions or SUSARs) according to the regulatory-defined timelines (7-day or 15-day reports). [name] will copy Astex pharmaceuticals (SGI-110 manufacturer) on any such reports.

In accordance with the regulation 21 CFR § 312.33, the IND Sponsor shall within 60 days of the anniversary date that the IND went into effect submit a brief report of the adverse events and progress of the investigation. All IND annual reports will be submitted to the FDA by the IND Sponsor.

Events will be reported to the FDA using Form FDA 3500A (Mandatory Reporting Form for investigational agents) or FDA Form 3500 (Voluntary Reporting Form for commercial agents). Forms are available at <http://www.fda.gov/medwatch/getforms.htm>.

#### *7 Calendar-Day Telephone or Fax Report:*

The IND Sponsor is required to notify the FDA of any fatal or life-threatening adverse event that is unexpected and assessed by the investigator to be possibly related to the investigational agent. Such reports are to be telephoned or faxed [contact]) to the FDA within 7 calendar days of first learning of the event.

#### *15 Calendar-Day Written Report:*

The IND Sponsor is required to notify the FDA of any serious adverse event that is unexpected and possibly related to the investigational agent in a written IND Safety Report.

Written IND Safety Reports should include an Analysis of Similar Events in accordance with regulation 21 CFR § 312.32. All safety reports previously filed with the IND concerning similar events should be analyzed. The new report should contain comments on the significance of the new event in light of the previous, similar reports. Written IND safety reports with Analysis of Similar Events are to be submitted to the FDA within 15 calendar days of first learning of the event.

CONFIDENTIAL

This document is confidential. Do not disclose or use except as authorized.

## 11.7 Reporting to Hospital Risk Management

Participating investigators will report to their local Risk Management office any subject safety reports or sentinel events that require reporting according to institutional policy.

## 11.8 Monitoring of Adverse Events and Period of Observation

All adverse events, both serious and non-serious, and deaths that are encountered from initiation of study intervention, throughout the study, and within 30 days of the last study intervention should be followed to their resolution, or until the participating investigator assesses them as stable, or the participating investigator determines the event to be irreversible, or the participant is lost to follow-up. The presence and resolution of AEs and SAEs (with dates) should be documented on the appropriate case report form and recorded in the participant's medical record to facilitate source data verification.

For some SAEs, the study sponsor or designee may follow-up by telephone, fax, and/or monitoring visit to obtain additional case details deemed necessary to appropriately evaluate the SAE report (e.g., hospital discharge summary, consultant report, or autopsy report).

Participants should be instructed to report any serious post-study event(s) that might reasonably be related to participation in this study. Participating investigators should notify the Overall Principal Investigator and their respective IRB of any unanticipated death or adverse event occurring after a participant has discontinued or terminated study participation that may reasonably be related to the study.

## 12 DATA AND SAFETY MONITORING

Adverse event lists, guidelines, and instructions for AE reporting can be found in Section 11.0 (Adverse Events: List and Reporting Requirements).

### 12.1 Data Reporting

12.1.1 This is a Level II study under the SKCCC Data Safety Monitoring Plan. Data monitoring of this protocol will occur on a regular basis with the frequency dependent on the rate of subject accrual and the progress of the study. The protocol will be monitored internally at SKCCC by [name] and externally by the SKCCC CRO QA Office and the Coordinating Center in accordance with the JHU SKCCC Data Safety Monitoring Plan. Outside sites, USC, VUmc, and MSKCCC will use their internal clinical research offices to monitor their study patients and regulatory documents. Outside sites will provide copies of monitoring reports to the coordinating center. Eligibility for both sites will be monitored by the SKCCC CRO as well.

All trial monitoring and reporting will be done through the Safety Monitoring Committee (SMC) at SKCCC.

CONFIDENTIAL

This document is confidential. Do not disclose or use except as authorized.

Authorized representatives of the Coordinating Center may visit any satellite sites connected to the outside sites to perform audits or inspections, including source data verification. The purpose of these audits or inspections is to systematically and independently examine all trial-related activities and documents to determine whether these activities were conducted and data were recorded, analyzed, and accurately reported according to the protocol, Good Clinical Practice (GCP), and any applicable regulatory requirements.

12.1.2 [name] will be holding the IND for this study. She will comply with all regulated reporting requirements to the FDA.

## **13 REGULATORY CONSIDERATIONS**

### **13.1 Protocol Review and Amendments**

This protocol, the proposed informed consent and all forms of participant information related to the study (e.g., advertisements used to recruit participants) and any other necessary documents must be submitted, reviewed and approved by a properly constituted IRB governing each study location.

Any changes made to the protocol must be submitted as amendments and must be approved by the IRB prior to implementation. Any changes in study conduct must be reported to the IRB. The Overall Principal Investigator (or Protocol Chair) will disseminate protocol amendment information to all participating investigators.

All decisions of the IRB concerning the conduct of the study must be made in writing.

### **13.2 Informed Consent**

All participants must be provided a consent form describing this study and providing sufficient information for participants to make an informed decision about their participation in this study. The formal consent of a participant, using the IRB approved consent form, must be obtained before the participant is involved in any study-related procedure. The consent form must be signed and dated by the participant or the participant's legally authorized representative, and by the person obtaining the consent. The participant must be given a copy of the signed and dated consent document. The original signed copy of the consent document must be retained in the medical record or research file.

### **13.3 Ethics and Good Clinical Practice (GCP)**

This study is to be conducted according to the following considerations, which represent good and sound research practice:

CONFIDENTIAL

This document is confidential. Do not disclose or use except as authorized.

- E6 Good Clinical Practice: Consolidated Guidance  
[www.fda.gov/downloads/RegulatoryInformation/Guidances/UCM129515.pdf](http://www.fda.gov/downloads/RegulatoryInformation/Guidances/UCM129515.pdf)
- US Code of Federal Regulations (CFR) governing clinical study conduct and ethical principles that have their origin in the Declaration of Helsinki
  - Title 21 Part 11 – Electronic Records; Electronic Signatures  
[www.access.gpo.gov/nara/cfr/waisidx\\_02/21cfr11\\_02.html](http://www.access.gpo.gov/nara/cfr/waisidx_02/21cfr11_02.html)
  - Title 21 Part 50 – Protection of Human Subjects  
[www.access.gpo.gov/nara/cfr/waisidx\\_02/21cfr50\\_02.html](http://www.access.gpo.gov/nara/cfr/waisidx_02/21cfr50_02.html)
  - Title 21 Part 54 – Financial Disclosure by Clinical Investigators  
[www.access.gpo.gov/nara/cfr/waisidx\\_02/21cfr54\\_02.html](http://www.access.gpo.gov/nara/cfr/waisidx_02/21cfr54_02.html)
  - Title 21 Part 56 – Institutional Review Boards  
[www.access.gpo.gov/nara/cfr/waisidx\\_02/21cfr56\\_02.html](http://www.access.gpo.gov/nara/cfr/waisidx_02/21cfr56_02.html)
  - Title 21 Part 312 – Investigational New Drug Application  
[www.access.gpo.gov/nara/cfr/waisidx\\_02/21cfr312\\_02.html](http://www.access.gpo.gov/nara/cfr/waisidx_02/21cfr312_02.html)
- State laws

It is understood that deviations from the protocol should be avoided, except when necessary to eliminate an immediate hazard to a research participant. In such case, the deviation must be reported to the IRB according to the local reporting policy.

### 13.4 Study Documentation

The investigator must prepare and maintain adequate and accurate case histories designed to record all observations and other data pertinent to the study for each research participant. This information enables the study to be fully documented and the study data to be subsequently verified.

Original source documents supporting entries in the case report forms include but are not limited to hospital records, clinical charts, laboratory and pharmacy records, recorded data from automated instruments, microfiches, photographic negatives, microfilm or magnetic media, and/or x-rays.

### 13.5 Records Retention

All study-related documents must be retained for the maximum period required by applicable federal regulations and guidelines or institutional policies.

### 13.6 Data Collection

CONFIDENTIAL

This document is confidential. Do not disclose or use except as authorized.

Data will be collected and reported on either paper case report forms (CRF) or through an internal data monitoring system, which will be determined prior to the start of the study.

### **13.7 Multi-center Guidelines**

This protocol will adhere to the policies and requirements of the SKCCC.

- The Overall Principal Investigator/Coordinating Center is responsible for distributing all IND Action Letters or Safety Reports to all participating institutions for submission to their individual IRBs for action as required.
- Mechanisms will be in place to ensure quality assurance, protocol compliance, and adverse event reporting at each site.
- Except in very unusual circumstances, each participating institution will order the agent(s) directly from the supplier. A participating site may order the agent(s) only after the initial IRB approval for the site has been forwarded to the Coordinating Center.

### **Multicenter Guidelines**

#### Protocol Chair ([name])

The Protocol Chair is responsible for performing the following tasks:

- Coordinating, developing, submitting, and obtaining approval for the protocol as well as its subsequent amendments.
- Assuring that all participating institutions are using the correct version of the protocol.
- Taking responsibility for the overall conduct of the study at all participating institutions and for monitoring the progress of the study.
- Reviewing and ensuring reporting of Serious Adverse Events (SAE)
- Reviewing data from all sites.

#### Coordinating Center

The Coordinating Center is responsible for performing the following tasks:

- Ensuring that IRB approval has been obtained at each participating site prior to the first patient registration at that site, and maintaining copies of IRB approvals from each site.
- Managing central patient registration.
- Collecting and compiling data from each site.
- Establishing procedures for documentation, reporting, and submitting of AE's and SAE's to the Protocol Chair, and all applicable parties.
- Facilitating audits by securing selected source documents and research records from participating sites for audit, or by auditing at participating sites.

#### Participating Sites

CONFIDENTIAL

This document is confidential. Do not disclose or use except as authorized.

Participating sites are responsible for performing the following tasks:

- Following the protocol as written, and the guidelines of Good Clinical Practice (GCP).
- Submitting data to the Coordinating Center.
- Registering all patients with the Coordinating Center by submitting patient registration form, and signed informed consent promptly.
- Providing sufficient experienced clinical and administrative staff and adequate facilities and equipment to conduct a collaborative trial according to the protocol.
- Maintaining regulatory binders on site and providing copies of all required documents to the Coordinating Center.
- Collecting and submitting data according to the schedule specified by the protocol.

## 14 STATISTICAL CONSIDERATIONS

The hypothesis of this study is that SGI-110, a demethylating agent, can sensitize pretreated metastatic colorectal cancer patients to retreatment with irinotecan.

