### 3. PARTICIPANT SELECTION

#### 3.1 Eligibility Criteria

3.1.1 Participants must meet the following criteria on screening examination to be eligible to participate in the study:

- 3.1.2 Participants must have histologically or cytologically confirmed adenocarcinoma of the colon or rectum
- 3.1.3 Patients in the phase I cohort must have biopsiable disease and be amenable to having two research biopsies
- 3.1.4 Archival tissue must be procured if available
- 3.1.5 Participants must have measurable disease, defined as at least one lesion that can be accurately measured in at least one dimension (longest diameter to be recorded) as  $\geq 20$  mm with conventional techniques or as  $\geq$

CONFIDENTIAL

This document is confidential. Do not disclose or use except as authorized.

10 mm with spiral CT scan. See section 10 for the evaluation of measurable disease.

3.1.6 Patients in the phase II cohort must have progressed while receiving irinotecan therapy in the metastatic setting. There are no limitations on number of prior therapies in the metastatic setting.

3.1.7 Age minimum of 18 years.

Because no dosing or adverse event data are currently available on the use of SGI-110 in participants <18 years of age, children are excluded from this study but will be eligible for future pediatric trials.

3.1.8 Life expectancy of greater than 12 weeks.

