#### **4.3 Patient assignment and randomization procedure for second cohort**

Each subject who satisfies the eligibility criteria and is accepted for the study will be assigned a unique identification number. The subject number will be used to identify the subject throughout the study and will be entered on all study documents. Once the subject identification number has been assigned, a confirmation email will be sent to all site personnel.

For the Randomized Cohort, subjects will be randomized to each treatment arm (SGI-110+irinotecan or regorafenib/TAS-102) prior to treatment administration and should not exceed 1 week of the planned dose. The assignment will not be blinded. Randomization will be stratified by standard treatment (Regorafenib or TAS-102) and time from last irinotecan treatment (> 6 months or < 6 months) through a dynamic algorithm to maintain balance between the arms as much as possible. For those assigned to treatment arm with standard of care therapy will receive regorafenib (if previously received TAS-102) or TAS-102 (if previously received regorafenib). If they have never received either regorafenib or TAS-102, choice of therapy will be deferred to treating physician and patient.

This is an open-label study. There will be no blinding of treatment assignment.

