### 14.1 Study Design/Endpoints

This is a Phase I/II study of Irinotecan and SGI-110 in patients with locally advanced or metastatic colorectal cancer. The dose escalation portion of the study will be used to determine the preferred dose of SGI-110, 30mg/m^2, 45 mg/m^2 or 60 mg/m^2, in combination with Irinotecan. The second portion of this study will be an open-label randomized phase II study with one arm receiving combination SGI-110 plus Irinotecan at the recommended dose from phase 1 (determined to be SGI-110 45mg/m^2, Irinotecan 125mg/m^2, with mandatory growth factor support) and the other arm receiving Regorafenib or TAS-102 at the standard commercial dose. The primary objective of the study is based on a comparison of PFS in the SGI-110 arm to that in the Regorafenib or TAS-102 arm, the two approved standard of care drugs in this setting. The primary endpoint for the Phase II study will be progression free survival (PFS). The study will randomize patients to the SGI-110 versus Regorafenib or TAS-102 at a ratio of 2:1. The randomized Regorafenib or TAS-102 group will provide information about PFS with the standard of care drugs to verify assumptions made in the design of the study.

**Phase I primary objective:** To assess safety and tolerability of Irinotecan in combination with SGI-110 in patients with advanced colon cancer. Determine the maximum tolerated dose (MTD) of Irinotecan in combination with SGI-110 and recommend a dose for phase II study.

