**Moving to Phase II Component:** Our hypothesis is that SGI-110 treatment will sensitize colon cancer patients to retreatment with irinotecan. Accordingly, it will be important to see that the dose of SGI-110 that is at the MTD does have pharmacodynamics effects at the tumor level. Patient tumor biopsies post-treatment will be analyzed by LINE assay for demethylation to assess for at least 10% demethylation from baseline in the tumor biopsies. We aim to see this level of demethylation in at least 60% of post-treatment biopsies as previously described in phase O studies.

**Phase II primary objective:** Evaluate the progression free survival (PFS) in patients receiving combination SGI-110 plus Irinotecan compared to standard of care treatment with regorafenib or TAS-102. Events are defined as disease progression or death from any cause. All patients treated

CONFIDENTIAL

This document is confidential. Do not disclose or use except as authorized.

on protocol will be included in the determination of PFS, regardless of treatment modification or discontinuation.

Epigenetic therapy may take several cycles to exert its maximal benefit, and preclinical data has demonstrated initial tumor growth is possible prior to tumor shrinkage. Patients on treatment with SGI-110 and IRI will be allowed to remain on study if their tumor progresses on RECIST 1.1 criteria if they are 1) clinically stable, 2) their provider feels it would be in their best interest, and 3) the patient is informed of scan results and consents to remain on treatment. In this circumstance, they will be reimaged on schedule after 2 further cycles. If this subsequent imaging confirms progressive disease, the date of the progression even will be dated to the first (initial) scan date that progression was first documented.

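### The stated hypothesis is sensitisation to irinotecan, but the PFS comparison tests only the regimen against standard care, and the analysis leaves out the stratification factors, including time since irinotecan

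*Combined protocol and SAP*

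**What the plan says.** **Hypothesis.** Section 14 opens with the hypothesis that "SGI-110, a demethylating agent, can sensitize pretreated metastatic colorectal cancer patients to retreatment with irinotecan". Section 14.1, Moving to Phase II Component, repeats it: "Our hypothesis is that SGI-110 treatment will sensitize colon cancer patients to retreatment with irinotecan".

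**Comparison.** In 14.1 one phase II arm receives SGI-110 plus irinotecan, with "the other arm receiving Regorafenib or TAS-102 at the standard commercial dose". The primary objective rests on a "comparison of PFS in the SGI-110 arm to that in the Regorafenib or TAS-102 arm". No arm gives irinotecan alone or SGI-110 alone.

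**Prior irinotecan.** Section 3.1.6 requires that patients "must have progressed while receiving irinotecan therapy in the metastatic setting" and adds: "There are no limitations on number of prior therapies in the metastatic setting". No maximum time since irinotecan is set. The only interval rule is the general 4-week chemotherapy washout in 3.2.2, which is a minimum.

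**Stratification.** Section 4.3 says: "Randomization will be stratified by standard treatment (Regorafenib or TAS-102) and time from last irinotecan treatment", split at 6 months. Stratification Factors in Section 14 repeats both factors, and 5.2.1 has the interval recorded at screening.

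**Analysis.** The primary analysis text in 14.1 describes life-table estimates by arm. The one-sided 0.05 log-rank test appears in the futility simulations and as item 1 of the secondary analyses. None of this text mentions the stratification factors, a Cox model or a PFS result by irinotecan interval.

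**The concern.** Sensitisation is a claim about what SGI-110 adds to irinotecan. Testing it by randomisation needs irinotecan in both arms. Here a PFS difference is the joint effect of SGI-110 and renewed irinotecan, relative to an active standard drug. Because time off irinotecan and intervening therapy are unlimited, the documents do not exclude some activity from rechallenge alone.

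Two things are at stake. First, a positive result could be read against a hypothesis that the comparison does not test. Second, the plan balances the arms on the irinotecan-free interval, the variable most relevant to this ambiguity, and then does not use it. That leaves the log-rank test unspecified with respect to the randomisation strata and gives the reader no view of whether the effect differs by interval.

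**Working it through.** **1. The plan's own figures.** From the operating-characteristics table in 14.1, the overall probability of a positive trial is (1 − futility stop) × (rejection at the final analysis):
- HR 0.80: (1 − 0.128) × 0.220 = 19.2%
- HR 0.60: (1 − 0.052) × 0.688 = 65.2%
- HR 0.526: (1 − 0.020) × 0.847 = 83.0%

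The table is internally exact. These probabilities apply whichever drug produces the hazard ratio; the test cannot tell.

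A direct check of the 83% uses power = Φ(|ln HR| × √(d × 2/3 × 1/3) − 1.645). With d = 96 events this is Φ(0.642 × 4.619 − 1.645) = Φ(1.32) = 90.7%. The plan gives no event count; 76 events would give 84.0%. The stated power is thus conservative against these inputs, and nothing below depends on it.

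**2. Illustration: SGI-110 inert, irinotecan active only in patients over 6 months off it.** From the plan: 64 versus 32 patients, control median 1.9 months, one-sided 5%. Assumed: exponential PFS, no censoring, no futility look, the share of patients over 6 months, and the rechallenge hazard ratio in them (1.0 in the rest). Percentage of 4,000 simulated trials that are positive:

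| Assumed rechallenge HR | 30% over 6 months | 50% | 70% |
|---|---|---|---|
| 0.526 | 26% | 47% | 69% |
| 0.70 | 14% | 23% | 32% |

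A repeat with 6,000 runs gave 25, 48 and 70%, and 14, 22 and 33%. With no effect in anyone the rate is about 6%. Stratifying the test by interval changes the first row to about 20, 38 and 62%. Stratification therefore does not solve attribution; its purpose is to match the analysis to the randomisation.

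**3. Precision within an interval stratum.** With nearly all patients having an event, SE(ln HR) ≈ √(1/n_A + 1/n_B), and the 95% CI factor is exp(1.96 × SE).
- Half of patients (32 vs 16): SE = √(1/32 + 1/16) = 0.306, factor 1.82
- 30% (about 19 vs 10): SE = √(1/19.2 + 1/9.6) = 0.395, factor 2.17
- 70% (about 45 vs 22): SE = √(1/44.8 + 1/22.4) = 0.259, factor 1.66

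For the treatment-by-interval interaction with an even split, SE = √2 × 0.306 = 0.433. Even a contrast of HR 0.526 against 1.0 gives 0.642/0.433 = 1.48 standard errors, so power at two-sided 5% is about Φ(1.48 − 1.96) = 32%. These results can only be descriptive.

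**4. Cost of stratifying.** Simulated power at HR 0.526 in everyone (6,000 runs, even interval split, second factor assumed 50:50 and not prognostic, otherwise as in step 2):

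| Assumed hazard ratio between interval strata | No strata | Interval only | Both factors |
|---|---|---|---|
| 1 (not prognostic) | 90% | 90% | 87% |
| 2 | 87% | 90% | 88% |
| 3 | 82% | 90% | 88% |

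Stratifying by both factors costs about 3 points if neither matters and gains about 1 to 6 points if the interval is strongly prognostic.

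**The case against.** The strongest reply is that the primary objective in 14.1 already reads as the combination against regorafenib or TAS-102. This is correct: that comparison is randomised, valid and answerable. A reader might infer that the missing irinotecan control invalidates the primary analysis. The documents do not support that; comparator choice is a legitimate design decision, and the mismatch lies only between the hypothesis sentence and what is tested.

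Second, the repeated hypothesis in Moving to Phase II Component introduces a pharmacodynamic check (at least 10% LINE demethylation in at least 60% of post-treatment biopsies), not the PFS test. Section 8.3.1 also plans paired biopsies in 36 Arm A patients. These address mechanism and deserve credit. They can show that methylation changed, but not that the change produced a PFS gain.

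Third, every phase II patient has progressed on irinotecan, and 2.5 describes retreatment only with cetuximab added. This makes a rechallenge-only effect less likely without excluding it. The documents give no PFS for rechallenge alone, so the simulated percentages follow wholly from assumed effects. An assumed 0.526 equals the trial's full design effect and is an extreme case.

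Three further inferences are tempting and go too far:
- That the test is planned as unstratified. The text is silent.
- That stratifying by interval shows an expectation that irinotecan alone regains activity. The only stated purpose is balance, and ordinary prognostic balancing explains it equally well.
- That an effect in the under-6-month stratum would establish sensitisation. Both drugs still differ between the arms within that stratum, and an estimate below 1 would occur about half the time with no effect there.

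**Conclusion.** The point holds as a matter of alignment and analysis specification. The primary PFS comparison estimates the effect of the regimen against regorafenib or TAS-102. It does not test the sensitisation hypothesis in Section 14, and no analysis of this design can isolate SGI-110's share of a PFS difference. Separately, two factors used to stratify randomisation do not appear in the analysis text, and no PFS result by irinotecan interval is planned.

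A reader might infer that a positive trial would probably reflect rechallenge, or that the report is bound to claim sensitisation. Neither follows: the documents contain no rechallenge estimate and no planned reporting text to that effect. The 14% to 69% range shows only that the ambiguity could matter if rechallenge had the assumed effects in the assumed shares of patients.

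**What to change.** 1. In 14.1, Analysis of primary objective, specify that the one-sided 0.05 log-rank test and a Cox model for PFS are stratified by the two randomisation factors. For this, the intended standard drug must be recorded before randomisation for Arm A patients as well, and an interval of exactly 6 months must be assigned to one category.
2. Report the PFS hazard ratio with 95% CI within each irinotecan-interval stratum, and the treatment-by-interval interaction, labelled descriptive only.
3. In Section 14, state that the randomised comparison tests SGI-110 plus irinotecan against standard care, that it does not isolate SGI-110's contribution from irinotecan rechallenge, and that any statement on sensitisation is hypothesis-generating whatever the stratum results.

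The cost is wording and one prespecified analysis on factors already used at randomisation, with no new arm, patients or visits. The downsides are a more modest claim, imprecise stratum estimates, and a loss of about 3 points of power if neither factor proves prognostic.
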